#### INTENSITY OF AES

The intensity of the AE will be characterized as mild, moderate, or severe.

Mild AEs are usually transient, require no special treatment, and do not interfere with the subject's daily activities.

Moderate AEs traditionally introduce a low level of inconvenience or concern to the subject and may interfere with daily activities but are usually ameliorated by simple therapeutic measures.

Severe AEs interrupt a subject's usual daily activity and typically require systemic drug therapy or other treatment.

When the intensity of the AE changes over time, the maximum intensity will be recorded.

#### RELATIONSHIP TO DEFINITY ADMINISTRATION

The relationship or association of the AE to the Definity administration will be characterized as "unlikely," "possible," or "probable." A relationship assessment will be performed by the investigator to determine if an AE is attributable to Definity and will be recorded on a data form. The investigator will refer to the Definity Package Insert for assistance in determining AE relationship.

An "unlikely" relationship indicates that there is little or no chance that Definity caused the reported AE; other conditions, including concurrent illnesses, progression or expression of the disease state, or a reaction to a concurrent medication, appear to explain the reported AE.

A "possible" relationship indicates that the association of the AE with Definity is unknown. However, the AE is not reasonably attributed to any other condition.

A "probable" relationship indicates that a reasonable temporal association exists between the AE and Definity administration and, based upon the investigator's clinical experience, the association of the event with the trial medication seems likely.

## SERIOUS ADVERSE EVENTS

A "serious" AE (SAE) is defined as a significant clinical hazard, contraindication, or precaution that:

Results in death

- Is life-threatening (In the opinion of the investigator, there is an immediate risk of death from the AE as it occurred. This does not include an AE that had it occurred in a more serious form may have caused death.)
- Results in a persistent or significant temporary disability/incapacity defined as a substantial disruption of a person's ability to conduct normal life functions
- Results in or prolongs an existing in-patient hospitalization (an overnight stay in the hospital, regardless of length) [Note: A hospitalization for an elective procedure or treatment which is not associated with an AE, hospitalization for a pre-existing condition which did not worsen, and hospitalization for reasons of convenience or observation, do not constitute an SAE.]
- Is a congenital anomaly/birth defect (in offspring of a subject taking the trial medication, regardless of time to diagnosis)
- Is an important medical event that may not result in death, be life-threatening, or require hospitalization but based upon the appropriate medical judgment, the event may jeopardize the subject and may require medical or surgical intervention to prevent one of the outcomes listed for the definition of a serious adverse experience.

All unexpected and serious adverse events are reported to the TJU IRB and to FDA if applicable.

The investigator is required to submit all unexpected and serious adverse events to the TJU IRB and the

data safety monitoring board within 48 hours. Fatal adverse events related to treatment which are unexpected must be reported within 24 hours to the TJU IRB and the DSMB through CTSO.

The written report for any SAEs that occur during the study, whether or not related to the Definity administration will be submitted immediately (within 24 hours) to the TJU Institutional Review Board.

The designated medical monitor will review all serious and unexpected adverse events associated with the protocol and provide an unbiased written report of the event within 10 calendar days of the initial report. At a minimum, the medical monitor will comment on the outcomes of the adverse event and relationship of the event to the Definity administration.

A copy of the SAE will be retained on file with the respective subject's data forms.

## 6.7 End-of-Treatment and End-of-Trial Evaluations

### 6.7.1 Discontinuation of Subjects

Subjects will be free to discontinue trial participation at any time. The investigator will also discontinue any subject from the trial if, in the investigator's opinion, it is not safe for the subject to continue. The date the subject is withdrawn from a treatment and/or from the trial and the reason for discontinuation will be recorded on the CRF.

Trial participation will be considered completed if the subject has met all of the trial requirements that is to participate in 4 US contrast studies during the duration of their clinical cancer treatment.

If a subject's participation in the trial is interrupted for any reason (e.g., because of an AE or if the subject is lost to follow-up) and the subject has met the criteria described above for completing the trial, the subject's trial participation will be considered completed. If a subject's trial participation is interrupted

for any reason by the subject's or investigator's choice and the subject has not met all of the criteria listed above, then the subject will be considered a discontinued subject.

## **7 Data Management And Statistical Analyses**

### **7.1 Data Management**

Data forms will be completed for all subjects enrolled in the trial. The patient study files will be stored in a secure file cabinet and maintained by the research study coordinator. Patient study files will be kept for 7 years after the completion of the study.

The final data will be entered into a database. The investigator will be responsible for management of the database. The database will be maintained within an organized and secure directory system.

### **7.2 Statistical Analyses**

#### **7.2.1 Hypotheses:**

H1: Our hypothesis is that subharmonic signals from US contrast microbubbles can be employed to image breast cancer neovascularity as well as noninvasively measure the IFP of breast cancer (i.e., using SHAPE) and that this information will improve the monitoring of tumor response to neoadjuvant therapies ultimately allowing for better, individualized treatment options to be selected. This in turn will result in improved clinical outcomes and greater survivability for women afflicted with breast cancer.

#### **7.2.2 Analysis of Results**

For the pre and post-contrast enhanced comparisons, dichotomous parameters (e.g., responder/non-responder) and ranked data (less, iso, or more intense) will be analyzed with the McNemar test which

measures significance of changes in related samples (pairwise comparisons). For variables in which accurate numerical measurement is possible (e.g., IFP and vascularity), the techniques will be compared using logistical regression and an ANOVA.

The ability of the imaging tests to distinguish responders from non-responders will be compared using ROC analysis, while the incremental validity of imaging assessments will be analyzed using logistic regression and ROC analyses. The tests are fundamental grayscale US imaging, PDI, 3D SHI and contrast enhanced MRI, while patient outcomes and pathology will provide the reference standards. All studies will be rated on a quasi-continuous scale from 0 to 100, since this has an intuitive probabilistic interpretation and improves the assessment of the characterization capabilities of the imaging modalities compared to using a coarser 6-point scale. Logistical regression techniques will be used to combine the 3 US imaging modes and MRI as well as to incorporate the quantitative parameters (i.e., SHAPE IFP estimates) into the US evaluation before repeating the ROC analysis. This will allow all possible combinations to be compared to one another (e.g., MRI versus all the US modes combined or MRI and grayscale US versus MRI and grayscale US and SHI, etc.). Differences between ROC curves will be tested by computing Mann-Whitney statistics.

All histopathological variables will be compared to imaging judgments of vascularity for the different modalities. When both sets of variables are nominal, chi-square tests will be conducted. When both types of variables are ordinal or continuous, correlations will be calculated. When one type of variable is nominal and one continuous non-parametric rank order tests such as Mann-Whitney U-tests or Kruskal-Wallis tests will be performed. Inter-observer variability will also be determined by calculating the intraclass correlation coefficient.

Comparisons of subject outcomes (i.e., responders vs. non-responders) established by monitoring the treatment with the different imaging modalities will be conducted with Cox Survival analysis (against

the pathological reference standard). For the US techniques where data from multiple time points are available, this analysis will be repeated for each time point. All of the statistical analyses proposed for the human clinical trial will be repeated split by racial and ethnic groups to determine if clinically important race/ethnicity differences exist in the ability of 3D SHI/SHAPE to monitor breast cancer treatment.

Finally, the vascularity measures obtained from the CD31 stained breast tumor specimens will be compared to the fractional tumor neovascularity data to determine if any correlation exists (in baseline PDI or contrast enhanced mode). The existence of a linear relationship between US and pathologic data will be assessed using single variable linear regression techniques and reverse stepwise multiple linear regression analysis.

All analyses and computations will be performed using Stata 12.0 (Stata Corporation, College Station, TX), while the study database will be designed and implemented in Filemaker Pro 10.0 (Filemaker Inc, Santa Clara, CA). This database will contain all patient information (except names and other identifiers) and the results of the various US imaging modes as well as the pathology results.

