#### *US Examination Protocol.*

A baseline ultrasound grayscale (US) scan of the treated lesion will be obtained and the following criteria assessed: the size, shape, and orientation of the site; echogenicity compared to surrounding tissue. Standard PDI of the LABC will also be performed. The distribution of color

signals and the overall color content of mass will be evaluated by comparing the pattern and amount of color to the normal surrounding breast. If uniform, the color will be categorized as less intense, iso-intense or more intense than normal breast. If non-uniform, the color will be described by location, intensity and distribution. Irregularity of the course of the vessels will be scored on a scale from 1.0 to 5.0 (smooth to severe irregularity) and anastomoses between adjacent vessels will be noted (as 1-2, 3-5 or >5 vessels connecting). The vascular pattern will also be graded as peripheral, radial from one or multiple sites, spotty or a combination. Digital clips of the two baseline imaging modes will be acquired.

The contrast administration will be an intravenous infusion of 2 vials of Definity/50ml saline through the subjects' vascular port (established as part of their standard of care), with infusion rates of 4 to 10 ml/min (titrated to effect). Next, we will run a power optimization algorithm to establish the individualized acoustic parameter settings for the case (on the first imaging study only). We will use those parameters for all subsequent imaging studies to sweep the area of the LABC to acquire 3D, pulse inversion SHI grayscale volume data. The digital clips and RF data obtained from each 3D SHI injection will be transferred to a PC for off-line analysis. The SHI images will be qualitatively analyzed as described above. This protocol will be followed for all the contrast studies for each subject (except for the power optimization algorithm, which will only be run once for each patient). All subjects will be closely monitored by a physician during and following the study.

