#### *Data Assessments.*

The pre- and then post-contrast US imaging will be evaluated for each patient at all 4 time points in one reading as follows: grayscale, grayscale and PDI (baseline), and grayscale and 3D SHI. While this may introduced some bias from pre- to post-contrast results, we considered this the

more realistic approach to how US contrast may be used in clinical practice. Each case will be read independently by the 2 experienced co-investigators (more than 15 years of expertise in breast imaging) blinded to the contrast-enhanced MRI evaluations, to allow repeatability to be assessed. All US studies will be rated on a quasi-continuous scale from 0 to 100 ranging from “no change relative to pre-therapy” over “indeterminate” to “definite changes seen.” Using a quasi-continuous 100-point rating scale has an intuitive probabilistic interpretation and is known to improve the assessment of the capabilities of the imaging modes studied.

Moreover, the 3D SHAPE results (i.e., IFP estimates) will be compared to lesion size, tumor response, DFS and overall survival. Results will also be compared to MRI enhancement kinetics and imaging measurements of lesion size obtained before and after completion of the chemotherapy. Once surgery has been performed the following variables estrogen, progesterone and HER2 receptor presence or absences; presence or absence of hemorrhagic, necrotic, or other component of the lesion (and their location if present); histological margins; lesion size; TNM staging; histological lesion type; presence or absence of vascular invasion; histological and cytological grade; presence or absence of metastases; node staging; and percentage of the lesion that was invasive or *in situ* will be collected as part of the patient’s clinical care and correlated with the imaging results. Finally, the ability of 3D SHI to image angiogenesis (specifically fractional tumor vascularity) will be compared to specimens stained for an immunohistochemical predictor of angiogenesis, specifically a monoclonal antibody against the PECAM endothelial cell marker (anti-CD31; Dako Corporation, Carpinteria, CA). The PI has developed the necessary software for quantitative analysis of contrast enhanced US images and specimens

stained with CD31 using a histomorphometry system based on an SMZ-10A microscope (Nikon, Melville, NY) and ImagePro Plus software.

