*Statistical Analysis.* Our statistical analysis will address the primary objective of this study by answering two major questions:

1. Can *in vivo* 3D SHAPE monitor the effect of neoadjuvant chemotherapy on breast cancer IFP?
2. Can *in vivo* 3D SHI monitor the effect of neoadjuvant chemotherapy (i.e., responders/non-responders) on breast cancer?

The findings of SHI/SHAPE will be correlated to vascular morphology (i.e., tumor angiogenesis ascertained with CD31) and other pathological findings; including size, vascularity, presence or absence of receptors. For the pre and post-contrast enhanced comparisons, dichotomous parameters (e.g., responder/non-responder) and ranked data (less, iso, or more intense) will be analyzed with the McNemar test which measures significance of changes in related samples (pairwise comparisons) for each time point. For variables in which accurate numerical measurement is possible (e.g., IFP and vascularity), the techniques will be compared using repeated measures logistical regression and ANOVA.

To answer statistical question 2, the ability of the imaging tests to distinguish responders from non-responders will be compared using ROC analysis, while the incremental validity of combining imaging assessments will be analyzed using logistic regression and ROC analyses. The tests are fundamental grayscale US imaging, PDI, 3D SHI and contrast

enhanced MRI, while patient outcomes and pathology will provide the reference standards. A power analysis was performed using PASS 12 (NCSS, East Kaysville, UT) to estimate the number of cases required to produce clinically acceptable results. A sample size of 20 responders and 20 non-responders (i.e., approximately halfway between 20 and 50 subjects) achieve 80% power to detect a difference of 0.174 between a diagnostic test with an area under the ROC curve ( $A_z$ ) of 0.800 (the null hypothesis) and an actual  $A_z$  of 0.974 using a one sample, two-sided z-test with a significance level of 0.05. The ratio of the standard deviation of the responses in the two groups was assumed to be 1.00. All analyses will be performed with Stata 12.0 (Stata Corp., College Station, TX).

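### McNemar on raw pre/post-contrast responder calls tests a change in call rate, not in accuracy, and no extension or cut-point is named for the three-level intensity ranking

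*Combined protocol and SAP*

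**What the plan says.** Section 7.2.2 (Analysis of Results) sets the rule for comparing readings before and after contrast: "dichotomous parameters (e.g., responder/non-responder) and ranked data (less, iso, or more intense) will be analyzed with the McNemar test". The Statistical Analysis paragraph of section 4 (Research Strategy) repeats it and describes the test as one that "measures significance of changes in related samples (pairwise comparisons) for each time point". Neither place says that a call is first scored as correct or incorrect.

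Three other statements define the inputs:

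- **Reader output** (Data Assessments): "All US studies will be rated on a quasi-continuous scale from 0 to 100". No rule turns this rating into a responder/non-responder call.
- **Intensity ranking** (US Examination Protocol): "If uniform, the color will be categorized as less intense, iso-intense or more intense than normal breast". Non-uniform colour is described in other terms and gets no rank.
- **Accuracy** (section 7.2.2): "The ability of the imaging tests to distinguish responders from non-responders will be compared using ROC analysis", and for that analysis "patient outcomes and pathology will provide the reference standards". The reference standards are not linked to the McNemar test.

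**The concern.** The hypothesis in section 7.2.1 is that the contrast information makes response monitoring better. A paired test on the calls themselves addresses a different question, namely whether readers say responder more or less often after contrast. A correction in a true responder moves the call one way and a correction in a true non-responder moves it the other way, so real improvements offset each other. Conversely, a reader who only becomes readier to say responder produces a significant change without any gain in accuracy. This second risk is concrete here, because pre- and post-contrast images are assessed in one reading and Data Assessments concedes that this may introduce bias.

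The intensity ranking has a separate problem. McNemar is defined for a 2×2 paired table and the ranking has three ordered levels. As written, the test cannot be run until someone chooses a cut or an extension, and that choice could be made after the data are seen.

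**Working it through.** **The plan's own figure.** The only power statement is for the area under the ROC curve, 0.800 against 0.974 with 20 + 20 patients. Using the binormal variance with SD ratio 1, SE₀ = 0.0775 and SE₁ = 0.0264. Power = Φ[(0.174 − 1.96 × 0.0775)/0.0264] ≈ Φ(0.84) = 79.9%, which reproduces the stated 80%. It concerns a different test and is untouched by this point. No power is given for McNemar.

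**Inputs.** The 20 + 20 split comes from the Statistical Analysis paragraph of section 4. All call patterns below are assumptions, since the documents give no paired call rates.

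**Formula.** With b and c discordant pairs and n = b + c, the exact two-sided p is 2 × Σ C(n,k) × 0.5ⁿ for k = 0 to min(b,c), capped at 1.

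**Case 1: real improvement.** Contrast corrects 6 responders (call moves to responder) and 6 non-responders (call moves to non-responder).

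- Raw calls: 6 vs 6, p = 1.00.
- Correct/incorrect: 12 vs 0, p = 2 × 0.5¹² = 0.0005.
- Sensitivity alone: 6 vs 0 of 20, p = 2 × 0.5⁶ = 0.031.

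**Case 2: threshold shift.** Contrast adds 10 responder calls, 5 in true responders and 5 in true non-responders.

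- Raw calls: 10 vs 0, p = 2 × 0.5¹⁰ = 0.002.
- Correct/incorrect: 5 vs 5, p = 1.00.

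**Simulation.** 20,000 runs, 20 + 20 patients, exact test at 0.05, pre and post calls assumed independent given true status:

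| Sensitivity/specificity, pre → post | Significant on raw calls | Significant on correct/incorrect |
|---|---|---|
| 0.6/0.6 → 0.9/0.9 | 1.6% | 83.7% |
| 0.7/0.7 → 0.9/0.9 | 1.8% | 50.5% |
| 0.6/0.8 → 0.9/0.5 (accuracy 0.70 both times) | 79.3% | 1.5% |

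The first row can be checked by expected counts. In responders, the chance of moving to a responder call is 0.4 × 0.9 = 0.36 and the chance of the reverse is 0.6 × 0.1 = 0.06. Non-responders mirror this. Raw discordance is therefore 20 × (0.36 + 0.06) = 8.4 in each direction, while correctness gives 20 × (0.36 + 0.36) = 14.4 against 20 × (0.06 + 0.06) = 2.4.

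**Three levels.** Illustrative paired table, n = 40, rows pre and columns post in the order less, iso, more: [6, 9, 0], [1, 8, 3], [0, 3, 10].

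- Cut at less vs iso/more: 9 vs 1, p = 2 × (1 + 10)/1024 = 0.021.
- Cut at less/iso vs more: 3 vs 3, p = 1.00.
- Bowker symmetry: (9 − 1)²/10 = 6.4 on 3 df, p = 0.094.
- Stuart-Maxwell homogeneity: 6.4 on 2 df, p = 0.041.

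One table thus gives p from 0.021 to 1.00, depending on a choice the plan does not make.

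**The case against.** The strongest reply is that accuracy is already tested. Grayscale, PDI, 3D SHI and MRI are compared by ROC analysis against outcomes and pathology, differences between curves are tested, and that is the only powered analysis. This stands. A reader might infer from the cases above that the trial could miss a true gain in accuracy altogether. The documents do not support that, because the ROC comparison is designed to show such a gain.

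It can also be said that the plan never presents McNemar as a test of correctness. It calls it a test of paired change, which describes the test correctly. That stands too: the test is not misdescribed, but what it measures is not what the hypothesis asks.

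A reader might further infer that no McNemar-type test exists for three levels. That is too strong. Bowker and Stuart-Maxwell are standard generalisations, although both ignore the order of the levels. The fault is only that the plan names neither of them, nor a cut-point.

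Finally, exact cancellation needs symmetric corrections, and the call patterns are invented. That is true of the two worked cases. The simulation imposes no exact cancellation within a run and still separates the two tests widely, though its scenarios are also assumed.

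**Conclusion.** The point holds for the McNemar line of the pre- versus post-contrast comparison and no further. On raw calls the test can return p = 1.00 when 12 of 40 calls are corrected, and p = 0.002 when overall accuracy is unchanged. Those sizes rest on the planned 20 + 20 split and on hypothetical call patterns. The direction of the problem follows from the test itself. The practical risk is a set of p-values, repeated by time point under section 4 and by racial and ethnic group under section 7.2.2, that contradict the ROC result. The ranked comparison cannot be run as written without a further decision. The sample size and the ROC analysis are unaffected. The wording should be corrected before analysis.

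**What to change.** Amend section 7.2.2 and the matching paragraph of section 4:

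1. **Calls.** Score each pre- and post-contrast call as correct or incorrect against the reference standard, then apply exact McNemar. Report sensitivity in responders and specificity in non-responders, so that a trade-off such as Case 2 is visible.
2. **Cut-off.** State the cut-off on the 0–100 scale and fix it before ratings are linked to pathology. The midpoint is not an obvious default: the scale runs from no change, through indeterminate, to definite change, so its middle lies around the indeterminate anchor, and it rates visible change rather than response directly.
3. **Intensity.** Replace McNemar with a paired ordinal test such as the Wilcoxon signed-rank test, in patients with uniform colour at both readings, and report how many are excluded.

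No new data are needed. The cost is precision. With about 20 per group, exact McNemar needs at least 6 one-directional changes to reach p < 0.05 (6–0 gives 0.031; 5–0 gives 2 × 0.5⁵ = 0.063). At the minimum enrolment of 20, an even split leaves 10 per group. The split results should therefore be presented as estimates with confidence intervals rather than judged on p-values. Restricting the ranking to uniform colour also loses patients, in a number the documents do not let one predict.

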### *Patient Enrollment*

At TJU, [name] (the medical oncologist on this project) and her colleagues treat more than 500 women with breast cancer each year out of which 1-2 women/week will be treated with neoadjuvant chemotherapy. We expect to enroll between 20 and 50 subjects undergoing neoadjuvant chemotherapy (i.e., 10 – 25 women/year) in this *first-in-humans* project who will be studied with contrast US (SHI and SHAPE) before as well as with around 10 % and 60% of the neoadjuvant chemotherapy treatment delivered and after completion of the last chemotherapy treatment. Thus, a total of some 144 contrast studies will be performed in this project (range: 80 – 200). The patients studied in this project will be women over the age of 21, who will receive an MRI as part of their standard of care (before and after completion of the chemotherapy). The MRI results together with pathology findings will be compared to the 3D SHI and SHAPE studies as a means for treatment monitoring.

Given that these women have been diagnosed with breast cancer, they are usually very motivated to participate in research studies that include additional monitoring and, therefore, we do not expect recruitment to be an issue. The patient population of this project will reflect the population demographics found at major American urban academic health centers. The overall hospital demographics for TJU include 60 % Caucasian, 16 % African American, 13 % Hispanic, 5 % Asian, 1 % Other, and 5 % unknown patients. Breast cancer in males accounts for only about 1% of cases at TJU and, thus, will not be included in the patient population.

The inclusion criteria for this trial are as follows:

- Females
- Be diagnosed with T1 or greater LABC, any N and M0.

- Be scheduled for neoadjuvant chemotherapy
- Be at least 21 years of age.
- Be medically stable.
- If a female of child-bearing potential, must have a negative pregnancy test.
- Have signed Informed Consent to participate in the study.

The exclusion criteria are:

- Males
- Females who are pregnant or nursing.
- Patients with other primary cancers requiring systemic treatment.
- Patients with any metastatic disease.
- Patients undergoing neoadjuvant endocrine therapy.
- Patients with known hypersensitivity or allergy to any component of Definity.
- Patients with cardiac shunts or congenital heart defects.
- Patients with unstable cardiopulmonary conditions or respiratory distress syndrome.

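### ROC areas of the logistic combinations are tested on the same patients used to fit them, which tilts non-nested comparisons such as MRI versus combined US towards the fitted combination

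*Combined protocol and SAP*

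**What the plan says.** Section 7.2.2 (Analysis of Results) sets out three steps.

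- Combinations are built by regression: "Logistical regression techniques will be used to combine the 3 US imaging modes and MRI as well as to incorporate the quantitative parameters", meaning the SHAPE pressure estimates.
- The ROC analysis is then repeated so that every combination can be compared with every other. One example given is "MRI versus all the US modes combined".
- The test is stated as: "Differences between ROC curves will be tested by computing Mann-Whitney statistics". The references cited for the ROC work include the nonparametric method for comparing correlated ROC areas.

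Section 4 (Statistical Analysis) places this under the second of the two questions that serve the primary objective: "the incremental validity of combining imaging assessments will be analyzed using logistic regression and ROC analyses".

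On numbers, Section 4 (Patient Enrollment) says "We expect to enroll between 20 and 50 subjects undergoing neoadjuvant chemotherapy", and the power statement uses "A sample size of 20 responders and 20 non-responders". The Synopsis, Section 4 and Section 7.2.2 mention no hold-out sample, cross-validation, optimism correction, shrinkage or weights fixed in advance.

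**The concern.** The nonparametric test of two ROC areas takes both scores as given before the data are seen. The combined US score is not given in that sense. Its three weights (grayscale, PDI, 3D SHI), or four with SHAPE, are chosen to separate the very responders and non-responders on whom its ROC curve is then drawn. MRI enters as one 0 to 100 rating. The area under its curve does not change under monotone rescaling, so it gains essentially nothing from fitting.

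Two things follow for a comparison of this non-nested kind. The reported Az of the combination is higher than it would be in new patients. The test's null also becomes equality of apparent areas rather than equality of discriminating ability, so part of any observed advantage over MRI is an artefact of fitting. A reader could conclude that combined US beats MRI when it does not. Section 7.2.2 also repeats all analyses within racial and ethnic groups, where there are fewer patients per fitted weight.

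**Working it through.** **1. The plan's own figure.** The power statement claims "80% power to detect a difference of 0.174 between a diagnostic test with an area under the ROC curve" of 0.800 and an actual 0.974, by a "one sample, two-sided z-test with a significance level of 0.05", with 20 per group and an SD ratio of 1.00. Use the binormal variance V(A) = 0.0099·exp(−a²/2)·[(5a² + 8) + (a² + 8)/R], with a = √2·Φ⁻¹(A) and R = 1.

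- V(0.800) = 0.1194, so the null SE is √(0.1194/20) = 0.0773.
- V(0.974) = 0.0139, so the alternative SE is √(0.0139/20) = 0.0264.
- Power = Φ[(0.174 − 1.96 × 0.0773)/0.0264] = Φ(0.85), about 80%.

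The figure reproduces. It concerns one test against a fixed benchmark and says nothing about fitted combinations.

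**2. Simulation inputs.** From the documents: 20 + 20 patients (range 20 to 50 in total), two-sided 0.05 (so 2.5% in the direction favouring US), SD ratio 1, three US inputs or four with SHAPE, and one MRI rating. Assumed, because the documents give no values: normal scores, equally informative US inputs, correlation 0.5 among them and 0.3 with MRI, and Az near 0.80. The Mann-Whitney test is read as the paired nonparametric test of correlated areas.

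**3. Quantities.** With mean shifts δ, covariance Σ and fitted weights b:

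- best possible Az = Φ[√(δ′Σ⁻¹δ/2)];
- Az of the fitted rule in new patients = Φ[b′δ/√(2b′Σb)];
- apparent Az = the Mann-Whitney area of the fitted score in the fitting sample.

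**4. Overstatement of Az.** Best possible combination and MRI both at 0.80; 500 data sets per row. Bootstrap correction: apparent Az minus the average, over resamples, of (Az of the refitted rule in the resample − Az of that rule in the original data).

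| Patients | Inputs | Apparent | New patients | Corrected |
|---|---|---|---|---|
| 20 | 3 | 0.848 | 0.750 | 0.769 |
| 20 | 4 | 0.873 | 0.731 | 0.775 |
| 40 | 3 | 0.823 | 0.776 | 0.778 |
| 40 | 4 | 0.836 | 0.767 | 0.776 |
| 50 | 3 | 0.817 | 0.780 | 0.781 |
| 50 | 4 | 0.825 | 0.771 | 0.774 |

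**5. False findings that US is better than MRI, 40 patients (nominal 2.5%).** The answer depends on what counts as no difference.

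| No difference means | 3 modes | With SHAPE |
|---|---|---|
| Fitted rule equals MRI in new patients | 7.1 to 7.4% | 11.1 to 12.9% |
| MRI equals the best possible combination | 4.0 to 4.3% | 5.2 to 5.6% |

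In the first row this is 7.1/2.5 = 2.8 and 11.1/2.5 = 4.4 times nominal at the lower ends. In the second, over 20,000 data sets, 4.3/2.5 = 1.7 and 5.6/2.5 = 2.2 times. Total two-sided rejection in that second case is 5.3% and 6.3%, because the error mostly moves to the side favouring US.

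**6. Is fitting the cause?** With weights known in advance, the same test finds US better in 2.0 to 2.7% of data sets, close to nominal.

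**7. Remedies, 40 patients.** Where the fitted rule equals MRI (Az 0.80) in new patients, the corrected difference over the usual standard error cut false findings for US from 6.4% to 3.2% (three modes) and from 10.0% to 3.8% (with SHAPE). Corrected Az was 0.807 and 0.805, against true values of 0.803 and 0.799. Leave-one-out scores overshoot: with MRI equal to the best combination, their mean Az was 0.738 and 0.727, against 0.776 and 0.765 in new patients, and US was called worse in 11.9% and 14.0% of data sets. Some of those calls are right, since the fitted rule is then slightly worse than MRI, but the Az is biased low by about 0.04.

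**The case against.** The strongest reply is that the effect on error rates may be modest. If MRI equals the best possible US combination, total rejection for the three modes stays near 5%. At Az 0.9 with 20 patients the excess disappears: three modes gave 2.4% even under the new-patient definition, and less than nominal under the stricter one. The study is also small and first-in-humans, its power statement does not concern combinations, and no trial decision is tied to combined US against MRI. All of this stands and limits the size of the point. It does not remove the overstated Az, which appeared at every sample size in the table.

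A reader might infer three stronger claims that the documents do not support.

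- *A fixed multiple, such as two to five times too many false findings for US.* Over Az 0.7 to 0.9 and 20 to 50 patients, the ratio to 2.5% ran from 0.4 to 4.4 when MRI equals the best combination, and from 1.0 to 7.6 when the fitted rule equals MRI in new patients. The largest values need low Az and four inputs. Section 1 cites a comparison that found MRI and US equivalent, and better than mammography, for residual disease, so near-chance settings are a poor guide.
- *That the same inflation affects nested comparisons*, such as the plan's other example of adding SHI to MRI and grayscale. With an uninformative SHI, the in-sample test rejected in 0.1% of data sets or fewer. That case is outside this point.
- *That the trial sets out to promote US over MRI.* The documents say only that results will be compared with MRI, and MRI is itself one of the inputs to be combined.

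**Conclusion.** The point holds for non-nested comparisons of a fitted combination with an unfitted test. As written, the plan would report combination Az values that are too high, by about 0.05 with three modes and 0.07 with SHAPE at 40 patients, and would use a test that leans towards the combination. The tilt ranges from slight to several-fold, depending on the true Az values, the number of fitted inputs, the sample size and the definition of no difference. The figures rest on assumed correlations and Az values, and none can be derived from the documents alone. The change is worth making because these analyses serve a question under the primary objective and need no new data.

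**What to change.** In Section 7.2.2, keep the logistic combinations and add the following.

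- Repeat the entire fit within each bootstrap resample. Report an optimism-corrected Az for every combination, and label the uncorrected value as apparent and optimistic.
- For any comparison of a combination with a test or combination not nested in it, base the ROC difference and its interval on the corrected values, not on a Mann-Whitney test of the refitted score.
- Optionally, as a sensitivity analysis, test a combination whose weights are fixed in advance. Put all inputs, including SHAPE, on a common standardised scale with directions set beforehand. A plain average of raw 0 to 100 ratings with a standardised SHAPE change would give SHAPE almost no weight. Because the readings in Section 4 (Data Assessments) are cumulative, equal weights would also count grayscale three times, so the choice of weights should take that into account.
- Do not simply apply the same test to leave-one-out scores, which errs against US.

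The cost is SAP wording and a little more code. Reported Az for combinations will be lower. At the bottom of the enrolment range the correction is incomplete (with 20 patients and four inputs, 0.775 against a true 0.731), so results there should be presented as exploratory.
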